7.6.1.1 All Adverse Events

An overall summary of adverse events at subject level, including AEs, SAEs, death, hypoglycemia, treatment-related events, and events leading to the discontinuation of study medication, will be performed for the short-term double-blind treatment period. All adverse events

(serious and non-serious, excluding hypoglycemic events that are not reported as SAEs) will be summarized by system organ class, preferred term for the short-term double-blind treatment period. For the analyses of the short-term double-blind treatment period, the summary of AEs and analyses by SOC and PT will be performed using the data prior to rescue as well as the data regardless of rescue. In addition, a subject listing of all reported adverse events will be produced, displaying all events (including pre-treatment events) that occurred prior to the start date of long-term treatment period, if any. All adverse events (serious and non-serious) including all hypoglycemic events will also be summarized by treatment group, where applicable.

AEs and SAEs with an onset from Day 1 of short-term double-blind treatment up to and including 4 days and 30 days respectively, after the last dose date in the short-term double-blind treatment period (or up and including to the start date of the long-term treatment period whichever comes first) will be considered as occurring during the short-term double-blind treatment period.

In addition, the following summaries will be provided for the short-term double-blind treatment period (excluding hypoglycemic events that are not reported as SAEs):

- Most common adverse events by preferred term and treatment group (i.e., reported by $\geq 2\%$ of subjects in any treatment group),
- Adverse events by system organ class, preferred term, intensity, and treatment group,
- Adverse events related to study medication by system organ class, preferred term, and treatment group.
- Proportion of subjects with adverse events by SOC and PT in subgroups of subjects defined by age category (< 65 , ≥ 65 , and ≥ 75 yrs), gender, race, and female age category (≤ 50 and > 50 yrs).

In addition to analyses of event incidence at the subject level, recurrence analyses will be performed at the event level. In order to prepare these summaries, the CRF data will be processed to categorize each line of patient data as a new occurrence or a continuation of an existing event. This determination will be based upon onset and resolution dates. Each line of patient data will represent the maximum severity observed at the time of occurrence as well as the last known assessed relationship to study medication by the investigator.

The following summary information will be provided:

Total number and rate (exposure adjusted) of occurrences for all AEs occurring in at least 5% of the subjects treated.

Additionally, a listing will be provided displaying the unique instances of all AEs, i.e., after duplicates have been eliminated and overlapping and contiguous occurrences of the same event have been collapsed. Because of how hypoglycemic events are assessed and captured in the database, each reported event is assumed to be unique and multiple hypoglycemic events will not be collapsed.

Similar analyses of adverse events will be performed for the combined short- and long-term treatment period. AEs and SAEs with an onset from Day 1 of short-term double-blind treatment up to and including 4 days and 30 days respectively, after the last dose date in the short- or

long-term treatment period will be included in summaries of the combined short- and long-term treatment periods.

No formal comparisons will be made between treatments. No formal statistical testing will be performed, only summary statistics will be provided.

7.6.2 Deaths

All deaths recorded on the status page, the AE page, or SAE page (with a death date, cause of death, outcome, or SAE categorization present) of the CRF will be used to identify deaths for the analyses. Any deaths that occur during the study will be described in depth as narrative in the CSR. A listing of all deaths that occur prior to the start date of long-term treatment period will be produced for the short-term treatment period and listing of all deaths that occur during the study will be produced for the combined short- and long-term treatment period.

7.6.3 Serious Adverse Events

All SAEs (including hypoglycemic events) will be described in narratives, regardless of investigator assessment of causality.

SAEs with an onset from Day 1 of short-term double-blind treatment up to and including 30 days after the last dose date in the short-term double-blind treatment period (or up to the start date of the long-term treatment period whichever comes first) will be considered as occurring during the short-term double-blind treatment period.

SAEs with an onset from Day 1 of short-term treatment up to and including 30 days after the last dose date in the short- or long-term treatment period will be considered as occurring during the combined short- and long-term treatment periods.

SAEs occurring during the short-term or combined short- and long-term treatment periods will be summarized by system organ class, preferred term, and treatment group for both the primary and sensitivity safety analyses. In addition, the proportion of subjects with related SAEs will be presented by system organ class, preferred term, and treatment group.

At the time of the ST+LT analysis two SAE listings will be produced: A listing of all SAEs for the short-term treatment period will be produced, displaying all SAEs (including pre-treatment events) that occurred prior to or on the start date of long-term treatment period, as well as listing of all SAEs for the combined short- and long-term treatment period will be produced, displaying all SAEs (including pre-treatment events) that occurred during the study.

7.6.4 Adverse Events Leading to Discontinuation of Study Medication

AEs with an onset during the short-term double-blind treatment period reported with an action taken of discontinuation of study medication will be summarized by system organ class, preferred term and treatment group for both the primary and sensitivity safety analyses. This summary will include hypoglycemia events that reported as SAEs. AEs leading to discontinuation during the short-term double-blind treatment period with an onset date on or prior to the start date of the long-term treatment period will be summarized. In addition, a subject listing of discontinuations due to AEs will be provided, displaying all events that led to discontinuation.

AEs with an onset during the combined short- and long-term treatment periods reported with an action taken of discontinuation of study medication will be summarized by SOC, PT, and treatment group for the primary safety analysis. This summary will include hypoglycemia events that reported as SAEs. When summarizing AEs leading to discontinuation for the combined short- and long-term treatment period, no upper cutoff day windows (i.e., 4 days and 30 days from last dosing date for AEs and SAEs, respectively) will be applied. In addition, a subject listing of discontinuations due to AEs will be provided, displaying all events that led to discontinuation.

7.6.5 Adverse Events of Special Interest (AEOSI)

Separate summaries will be provided for the following adverse events of special interest (AEOSI). Except as otherwise noted, to identify each type of other adverse event of special interest in this section, a list of PTs will be selected before database lock and unblinding of the database.

AEs and SAEs of special interest with an onset from Day 1 of short-term double-blind treatment up to and including 4 days and 30 days, respectively, after the last dose date in the short-term double-blind treatment period (or up to the start date of the long-term treatment period whichever comes first) will be considered as occurring during the short-term double-blind treatment period.

AEs and SAEs of special interest with an onset from Day 1 of short-term treatment up to and including 4 days and 30 days, respectively, after the last dose date in the short- or long-term treatment period will be considered as occurring during the combined short- and long-term treatment periods.

7.6.5.1 Hypoglycemia

Separate pages to capture events of hypoglycemia are contained within the CRF.

Hypoglycemic events with an onset from Day 1 of the short-term double-blind treatment up to and including 4 (30 days in case of SAEs) days after the last dose date in the short-term double-blind treatment period (or up to and including the start date of the long-term treatment period, whichever comes first) will be considered as occurring during the short-term double-blind treatment period. Hypoglycemic events with an onset from Day 1 of the short-term double-blind treatment up to and including 4 (30 days in case of SAEs) days after the last dose date in the long-term treatment period will be considered as occurring during the short-term plus long-term treatment period.

Hypoglycemic events will be categorized using two methods. One classification is based on the ADA recommendations² :

Severe hypoglycemia: “An event requiring assistance of another person to actively administer carbohydrate, glucagons, or other resuscitative actions. These episodes may be associated with sufficient neuroglycopenia to induce seizure or coma. Plasma glucose measurements may not be available during such an event, but neurological recovery attributable to the restoration of plasma glucose to normal is considered sufficient evidence that the event was induced by a low plasma glucose concentration.”²

Documented symptomatic hypoglycemia: “An event during which typical symptoms of hypoglycemia are accompanied by a measured plasma glucose concentration $\leq 70\text{mg/dl}$ (3.9mmol/l).”²

Asymptomatic hypoglycemia: “An event not accompanied by typical symptoms of hypoglycemia but with a measured plasma glucose concentration $\leq 70\text{mg/dl}$ (3.9mmol/l). Since the glycemic threshold for activation of glucagon and epinephrine secretion as glucose levels decline is normally $65\text{--}70\text{mg/dl}$ ($3.6\text{--}3.9\text{mmol/l}$) (24–26) and since antecedent plasma glucose concentrations of $\leq 70\text{mg/dl}$ (3.9mmol/l) reduce sympathoadrenal responses to subsequent hypoglycemia (1,11,20), this criterion sets the lower limit for the variation in plasma glucose in nondiabetic, nonpregnant individuals as the conservative lower limit for individuals with diabetes.”²

It is not medically possible for an event to be considered to be both asymptomatic hypoglycemia as well as severe hypoglycemia. In the ST+LT analysis, if an event is classified as both severe and asymptomatic, it will be considered only to be severe hypoglycemia in the summary tables. If an event is classified as both severe and as documented symptomatic hypoglycemia, even if unlikely but not deemed medically implausible, the event will be included in the summary tables under both classifications.

Probable symptomatic hypoglycemia: “An event during which symptoms of hypoglycemia are not accompanied by a plasma glucose determination (but that was presumably caused by a plasma glucose concentration $\leq 70\text{mg/dl}$ [3.9mmol/l]). Since many people with diabetes choose to treat symptoms with oral carbohydrate without a test of plasma glucose, it is important to recognize these events as “probable” hypoglycemia. Such self-reported episodes that are not confirmed by a contemporaneous low plasma glucose determination may not be suitable outcome measures for clinical studies that are aimed at evaluating therapy, but they should be reported.”²

Relative hypoglycemia: “An event during which the person with diabetes reports any of the typical symptoms of hypoglycemia, and interprets those as indicative of hypoglycemia, but with a measured plasma glucose concentration $> 70\text{mg/dl}$ (3.9mmol/l). This category reflects the fact that patients with chronically poor glycemic control can experience symptoms of hypoglycemia at plasma glucose levels $> 70\text{mg/dl}$ (3.9mmol/l) as plasma glucose concentrations decline toward that level (27,28). Though causing distress and interfering with the patient’s sense of well-being, and potentially limiting the achievement of optimal glycemic control, such episodes probably pose no direct harm and therefore may not be a suitable outcome measure for clinical studies that are aimed at evaluating therapy, but they should be reported.”²

The second classification of hypoglycemic events follows:

Major episodes of hypoglycemia - defined as symptomatic episodes requiring external (3rd-party) assistance due to severe impairment in consciousness or behavior with a capillary or plasma glucose value $< 3\text{ mmol/L}$ ($< 54\text{ mg/dL}$) and prompt recovery after glucose or glucagon administration

Minor episodes of hypoglycemia - defined as either a symptomatic episode with a capillary or plasma glucose measurement below 3.5 mmol/L (63 mg/dL) regardless of need for third-party

assistance or an asymptomatic capillary or plasma glucose measurement below 3.5 mmol/L (63 mg/dL), that does not qualify as a major episode

Other episodes of hypoglycemia - defined as episodes reported by the investigator that are suggestive of hypoglycemia but do not meet the above criteria.

All analyses of hypoglycemic events will be performed both overall and by each class of events both including and excluding rescue data, with the ADA classification system and excluding rescue data analysis serving as the primary analysis. All blood glucose measurements collected in the hypoglycemia module of CRF will be considered for classifying the hypoglycemia events irrespective of the method using which glucose data were collected.

The total number of events by treatment group will be summarized for the short-term double-blind treatment period, and the short-term and long-term treatment period. For short-term double-blind period analyses, the only upper cutoff date is 4 days (30 days in case of SAEs) following the date of the last dose of short-term double-blind study medication or the start of the long-term treatment period, whichever comes first. For the short-term and long-term treatment period, the upper cutoff date is 4 (30 days in case of SAEs) days following the date of the last dose of study medication.

Hypoglycemic events with an onset during the short-term double-blind treatment period and leading to discontinuation of study medication will be summarized by treatment group. A similar summary will be produced for the short-term and long-term treatment period. When summarizing hypoglycemic events leading to discontinuation, no upper cutoff day windows are applied.

A summary of the incidence of confirmed hypoglycemia, defined as blood glucose ≤ 70 mg/dL (3.9 mmol/L) recorded in the hypoglycemia module of the CRF, will be provided. Additionally, a summary will be provided for subjects who have at least one episode of confirmed hypoglycemia.

A listing of subjects will be produced, and it will display all hypoglycemic events with an onset date/time from the start date/time of short-term double-blind treatment period up to the start date of the long-term treatment period, and separately for the short-term and long-term treatment period.

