5 SAMPLE SIZE AND POWER

The mean change in baseline in HbA1c at Week 52 will be assessed by comparing saxagliptin, in co-administration with dapagliflozin, added to current background therapy with metformin, versus the active comparator treatment group (glimepiride added to current background therapy with metformin).

Power calculations for longitudinal repeated measures analyses depend on many factors, including the pattern of drop-outs over time and correlations among the various time points included in the model. The choice of these parameters will affect any estimates of power, and their true values may not be known. Based on comparisons of results of longitudinal repeated measures analyses and analysis of covariance using last observation carried forward (ANCOVA with LOCF) from previous diabetes trials, the estimated standard errors of the treatment differences were similar between analyses. Therefore, power calculations are based on ANCOVA with LOCF, with the expectation that this will provide a good estimate of the power for the primary analysis using a longitudinal repeated measures model.

Assuming a mean change from baseline in HbA1c difference effect of 0.35% for saxagliptin in co-administration with dapagliflozin plus metformin vs glimepiride plus metformin, a common standard deviation of 1.1%, and using a 2-sided significance level of 0.05 for the comparison, and assuming a 5% non-evaluability rate, then a sample size of 220 patients per arm will yield 90% power for the comparison of saxagliptin in co-administration with dapagliflozin plus metformin against glimepiride plus metformin.

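### The primary hypoglycaemia analysis stops at rescue but has no matching person-time denominator, so unequal rescue would understate hypoglycaemia in the more-rescued arm

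*SAP*

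**What the plan says.** SAP 7.6.5.1 runs the hypoglycaemia analyses with and without post-rescue data, "with the ADA classification system and excluding rescue data analysis serving as the primary analysis". SAP 7.6 and protocol 8.4.3 state the same priority. SAP 7.1.1.3 defines the pre-rescue window for safety data as ending on the day of the first rescue dose, subject to the post-treatment cut-off.

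The measures given in 7.6.5.1 are totals ("The total number of events by treatment group will be summarized for the short-term double-blind treatment period, and the short-term and long-term treatment period"), the incidence of confirmed hypoglycaemia, and a summary of subjects with at least one confirmed episode. SAP 4.4 describes the endpoint as a proportion plus frequency and severity. None of these is tied to person-time.

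Two other places bear on the point:
- SAP 7.6.1.1 plans, for general adverse events, "Total number and rate (exposure adjusted) of occurrences for all AEs occurring in at least 5% of the subjects treated". Under SAP 7.6.1, non-serious hypoglycaemia is not recorded on the AE page.
- SAP 7.4.1 already summarises exposure, both prior to rescue and regardless of rescue, for both the short-term and the combined period. It does not link that exposure to hypoglycaemia.

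**The concern.** Stopping the count at rescue makes time at risk depend on glycaemic failure. The trial expects glycaemic control to differ by arm (SAP section 1, research hypothesis). It also tests time to treatment intensification, which includes rescue, at 52 and 156 weeks (SAP 4.2), so unequal rescue is part of what the trial sets out to show. An arm with more rescue contributes fewer pre-rescue patient-years, and its event total and its proportion with an event fall for that reason alone.

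Confirmed hypoglycaemia is a named safety objective (SAP 3.4) and a central safety contrast with a sulfonylurea. The including-rescue analysis retains follow-up after rescue, but it adds events that occur on rescue therapy, for which insulin is the recommended first line (protocol 3.5.2). It therefore answers a different question and does not supply the missing denominator for the primary one.

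**Working it through.** **The plan's own sizing.** The only sizing figure is for HbA1c. Inputs from SAP section 5: "Assuming a mean change from baseline in HbA1c difference effect of 0.35" percentage points, "a common standard deviation of 1.1" percentage points, "using a 2-sided significance level of 0.05 for the comparison", "assuming a 5% non-evaluability rate", and the claim that "a sample size of 220 patients per arm will yield 90% power".
- n per arm = 2 × (1.960 + 1.282)² × 1.1² / 0.35² = 208 evaluable.
- 208 / 0.95 = 219 randomised, against 220 stated.
- 220 × 0.95 = 209 evaluable gives 90.2% power.

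The figure reproduces. Nothing is sized for hypoglycaemia.

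**Time at risk up to rescue.** The documents give neither rescue rates nor hypoglycaemia rates by arm. All values below are assumptions.

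For a proportion p rescued by time L with constant hazard, h = −ln(1 − p)/L, and mean time to the earlier of rescue or L is p/h. With the same true event rate in both arms, the ratio of expected event counts equals the ratio of mean times.

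*Week 52 (L = 1 year)*

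| Rescued, arm A vs B | Mean years, A | Mean years, B | Ratio B/A |
|---|---|---|---|
| 5% vs 10% | 0.975 | 0.949 | 0.97 |
| 10% vs 20% | 0.949 | 0.896 | 0.94 |

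*Week 156 (3 years), hazard changing at Week 52.* The rescue criterion moves from FPG to HbA1c at that point (protocol Table 3.5.2-1). Mean time = T1 + (1 − p1) × T2. T1 is the first-year term above, p1 is the proportion rescued by Week 52, and T2 uses the conditional proportion rescued over the next two years, 1 − (1 − p3)/(1 − p1), with p3 the proportion rescued by Week 156.

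| Rescued by Week 52 / Week 156, A vs B | Mean years, A | Mean years, B | Ratio B/A |
|---|---|---|---|
| 5% / 30% vs 10% / 50% | 0.975 + 0.95 × 1.723 = 2.61 | 0.949 + 0.90 × 1.512 = 2.31 | 0.88 |
| 10% / 40% vs 20% / 70% | 0.949 + 0.90 × 1.644 = 2.43 | 0.896 + 0.80 × 1.274 = 1.92 | 0.79 |

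*Week 156, constant hazard throughout.* 30% vs 50%: 2.164 / 2.523 = 0.86. 40% vs 70%: 1.744 / 2.349 = 0.74.

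**Effect on the planned summaries.** Take 220 per arm, a true rate λ = 0.5 events per patient-year in both arms, and 20% vs 40% rescued by Week 156 with constant hazard.
- Mean time at risk: 2.69 vs 2.35 years, ratio 0.87.
- Expected events: 220 × 0.5 × 2.689 = 296, vs 220 × 0.5 × 2.349 = 258.
- Subjects with at least one event, λ/(λ + h) × (1 − e^(−(λ+h)L)): 71.5% vs 64.6%.

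The true rate ratio is 1.00. Dividing events by pre-rescue patient-years returns 1.00.

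**Would it reverse a real difference?** With the same rescue rates, a true ratio of 3 against the more-rescued arm appears in counts as 3 × 2.349 / 2.689 = 2.62.

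**Early clustering.** Suppose the event rate is five times higher in the first 12 weeks (0.231 years) and rescue runs at a constant hazard over the remaining 2.769 years. For 20% vs 40% rescued the count ratio is (5 × 0.231 + 2.168) / (5 × 0.231 + 2.482) = 0.91 instead of 0.87.

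**Equal rescue.** The ratio is 1.00 whatever the level.

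**The case against.** Several points can fairly be made for the plan.

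- *An exposure-adjusted rate may already be intended.* A reader might infer that non-serious hypoglycaemia gets no such rate anywhere. The SAP does not establish that. Keeping events off the AE page is a data-collection rule, and 7.6.1.1 also plans an AE summary that includes all hypoglycaemic events and gives a no-collapsing rule for them beside the recurrence analysis. The text is ambiguous. What stands is that the rate is not clearly extended to non-serious hypoglycaemia and is not tied to pre-rescue data.
- *Exposure is reported and follow-up continues.* Pre-rescue exposure by arm will be tabulated, so an imbalance will be visible, and rescued subjects stay on blinded drug and in the visit schedule. The including-rescue analysis is a legitimate comparison, and insulin is recommended for rescue, not mandatory. This softens the point, but the primary summaries remain unadjusted.
- *Direction.* A reader might infer that the new regimen is made to look safer than it is. The documents do not support that: their hypothesis implies more rescue on glimepiride, so the error would run against the new regimen's expected advantage. The direction is still not guaranteed.
- *Size.* A reader might carry away a deficit of about a quarter. That is the Week 156 extreme under a constant hazard, although the rescue criteria change at Week 52. At Week 52 the deficit is about 3% to 6%.
- *Status.* Protocol 1.3.4 places hypoglycaemia under exploratory safety objectives, and no test is specified. This limits the consequence without making the summary accurate.

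**Conclusion.** The point holds as a weakness of the primary hypoglycaemia summary: it is truncated at rescue and has no denominator for the truncated window. Its size rests entirely on assumed rescue rates. With equal true event rates, the more-rescued arm's count would be low by about 3% to 6% at Week 52. At Week 156 it would be low by about 12% to 21% if the rescue hazard changes at Week 52, or 14% to 26% if it is constant. These figures also assume a constant hypoglycaemia rate; clustering during the 12-week glimepiride titration would make the deficit smaller. Under the study hypothesis glimepiride is the arm understated, so the difference between arms would be attenuated and not necessarily reversed. The point deserves action mainly for the 156-week report, where the effect could be material and the remedy is cheap.

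**What to change.** In SAP 7.6.5.1, for the excluding-rescue analysis, add events per 100 patient-years with 95% CI by arm, overall and by ADA class. Use one common denominator: first dose to the earlier of the first rescue dose or last dose + 4 days. Count events in that same window, so that every ADA class has the same exposure. SAEs falling only in the longer 30-day window can be shown separately.

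Keep the raw counts and the including-rescue analysis beside the rates. State whether the exposure-adjusted rate in 7.6.1.1 is meant to cover non-serious hypoglycaemia. A time-to-first-event curve censored at rescue may be added as supportive, with a note that rescue is triggered by hyperglycaemia and the censoring may therefore be informative.

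The cost is a little programming: the dates are collected and pre-rescue exposure is already derived under 7.4.1. SAP version 3 postdates the short-term CSR, so the change is prospective only for the 156-week report. Any Week 52 rates added now should be labelled post hoc.
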